### **5.1.4 Administration While on Plasma Exchange**

The rituximab infusion is to be given immediately after plasma exchange. The next plasma exchange is to be performed as late as possible in order to maximize exposure to rituximab. At least a 20-hour time interval between rituximab and plasma exchange is the goal. Plasma exchange is not to be performed sooner than 12 hours after the end of a rituximab infusion.

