#### **7.1.3 Toxicities associated with plasma exchange**

Subjects undergoing plasma exchange may experience the following side effects/complications:

- Complications secondary to vascular access including: hematoma, venous sclerosis, thrombosis and embolism, inadvertent arterial puncture, pneumothorax and/or hemothorax
- Vasovagal reaction
- Citrate toxicity including: circumoral paresthesias, nausea, vomiting, chills, muscular twitching, tetany, and syncope. Severe citrate toxicity may manifest as cardiac arrhythmia.
- Transfusion reaction associated with plasma, including: fever, chills, urticaria,
- Transfusion-related acute lung injury (TRALI)

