#### **7.1.4 Toxicities associated with corticosteroids**

The following adverse side effects may be seen in subjects on steroid therapy:

- Cardiovascular: arrhythmia, edema, hypertension
- Central nervous system: insomnia, delirium, psychoses, and seizures
- Dermatologic: hirsutism, skin atrophy, bruising, hyperpigmentation
- Endocrine and metabolic: glucose intolerance, Cushing's syndrome, pituitary adrenal axis suppression (adrenal insufficiency)

- Hematologic: transient leukocytosis
- Ocular: cataracts, glaucoma
- Miscellaneous: infections, hypersensitivity reactions, buffalo hump, moon face

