## 7.2 Relatedness to Participation in the Research Study

Each AE should be evaluated as to whether it was related or possibly related to participation in the research study (meaning that there is a reasonable possibility that the AE may have been caused by the procedures involved in the research). AEs determined to be solely caused by an underlying disease, disorder, or condition of the subject; or other circumstances unrelated to the research should be categorized as being not related to participation in the research.

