## 7.3 Relatedness to Use of the Study Drug (Rituximab)

Each AE should also be evaluated as to whether it was related to the use of rituximab:

Definite	An AE is clearly related to use of rituximab
Probable	An AE has a strong temporal relationship to use of rituximab, and another etiology is significantly less likely.
Possible	An AE has a strong temporal relationship to use of rituximab, and an alternative etiology is equally or less likely.
Unlikely	An AE has little or no temporal relationship to use of rituximab, and/or a more likely alternative etiology exists.
Not Related	An AE is not related to use of rituximab (no temporal relationship, or a much more likely alternative etiology exists).

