#### **7.4.4 Reporting Adverse Events to FDA**

All serious adverse events that are unexpected and possibly, probably, or definitely related to the use of rituximab will be reported to FDA no later than 7 days from the sponsor-investigator's original receipt of the information. FDA will receive annual summaries of all adverse events.

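### Section 7.3 grades a well-timed event Unlikely once one other cause ranks above rituximab, so an unexpected SAE to which rituximab plausibly contributed can miss expedited FDA and NHLBI reporting

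*Combined protocol and SAP*

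**What the plan says.** **The drug scale (7.3).** Three of the five grades matter here.

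- For Possible, the condition reads: "An AE has a strong temporal relationship to use of rituximab, and an alternative etiology is equally or less likely".
- One step lower, the condition for Unlikely reads: "An AE has little or no temporal relationship to use of rituximab, and/or a more likely alternative etiology exists".
- At the bottom of the scale, the bracketed explanation of Not Related reads: "no temporal relationship, or a much more likely alternative etiology exists".

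No grade covers a contributory cause, and there is no separate attribution to plasma exchange or corticosteroids.

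**The participation question (7.2).** An event is related or possibly related if "there is a reasonable possibility that the AE may have been caused by the procedures involved in the research". It is unrelated only when disease or circumstances outside the research are the sole cause.

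**Reporting.** Section 7.4.1 sends an unexpected SAE to the local IRB within 24 hours if it is at least possibly related either to rituximab or to participation. Section 7.4.2 requires immediate notice to NHLBI on rituximab relatedness only. Section 7.4.4 does the same for the 7-day report: "All serious adverse events that are unexpected and possibly, probably, or definitely related to the use of rituximab will be reported to FDA".

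**Overlapping exposures.** For subjects still on exchange, 5.1.4 says: "The rituximab infusion is to be given immediately after plasma exchange". Section 7.1.3 lists "Transfusion reaction associated with plasma, including: fever, chills, urticaria" among exchange complications, along with TRALI and arrhythmia. Section 7.1.4 lists "infections, hypersensitivity reactions, buffalo hump, moon face" for corticosteroids, along with arrhythmia.

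**Endpoint.** Sections 1.2.1 and 9.2 name treatment-related adverse events, without a scale or a cut-off grade.

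**The concern.** The two sections apply different standards to what can be the same event. Section 7.2 asks whether causation is reasonably possible. Section 7.3 ranks rituximab against alternatives, and a well-timed event drops below Possible as soon as one alternative ranks higher. In this trial, rituximab is given alongside two other treatments with partly overlapping toxicity, in a disease that can itself explain some findings, so such rankings will be needed.

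At stake is prompt external notice of a serious, unexpected event in a pilot study that has safety among its aims. Low-dose rituximab is proposed partly because it might carry fewer complications (2.4), so a rule that lowers attribution to the drug errs in the direction of that hypothesis.

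**Working it through.** The plan gives no figure to reproduce on this point. The check reads the grades as a decision rule, asks where rival causes are listed, and traces one event through each reporting route.

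**1. The grades as a rule, for an event with strong timing.** The percentages are assumed causal weights, used only to show where the boundary lies. Section 7.3 speaks of an alternative in the singular, so alternatives are compared with rituximab one at a time.

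| Rituximab | Alternatives | Grade under 7.3 |
|---|---|---|
| 50% | one at 50% | Possible |
| 49% | one at 100 − 49 = 51% | Unlikely (Not Related if much more likely) |
| 40% | one at 100 − 40 = 60% | Unlikely (Not Related if much more likely) |
| 40% | two at 30% each | Possible: neither ranks above rituximab |

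The boundary is therefore rank against a single competitor, not a fixed share. In the second and third rows a substantial contribution from rituximab is still graded below Possible.

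**2. Where a rival cause is listed.** Section 7.1.2 has 12 rituximab toxicity headings, leaving out vaccinations. By my classification:

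- Seven have a counterpart in 7.1.3 or 7.1.4: lung toxicity, severe infusion reactions, hypersensitivity, other infusion reactions, infections, cardiovascular reactions, and hepatitis B or other viral infection.
- One is partial: for hematologic events, TTP can explain thrombocytopenia and anemia but not lymphopenia or neutropenia.
- Four have none: renal, mucocutaneous, carcinogenesis and fertility, and most post-marketing terms. 7 + 1 + 4 = 12.

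This shows that an alternative is often available. It does not show that the alternative is more likely.

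**3. One event through each route.** Take an unexpected SAE with strong timing, a reasonable possibility that rituximab contributed, and one alternative ranked higher. The rituximab infusion is a research procedure, so 7.2 makes the event at least possibly related to participation, whether or not exchange also counts as one. Section 7.3 makes it Unlikely.

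| Route | Relatedness condition | Outcome |
|---|---|---|
| Local IRB, 24 hours (7.4.1) | rituximab or participation | reported |
| NHLBI, immediate (7.4.2) | rituximab only | not triggered |
| FDA, 7 days (7.4.4) | rituximab only | not triggered |
| Medical Monitor (7.4.2) | none | reviewed |
| Monthly SAE report (7.4.2) | none | included |
| Annual FDA summary (7.4.4) | none | included |

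The divergence in the first three rows follows from the text and needs no assumed rate.

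**4. How far it reaches.** Those three routes also require the event to be unexpected. Under 7.1.1, an event consistent in nature, severity and frequency with risks described in the protocol or labelling is expected. Most of the overlapping toxicities in step 2 are therefore outside these routes at any grade. What remains is the unexpected SAE, for example one more severe or more frequent than described. The documents give neither the rate of such events nor the share that would be graded Unlikely.

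**The case against.** The strongest reply is that 7.2 and 7.3 ask different questions, one about participation and one about the drug, so different standards are no contradiction. In addition, the plan anticipates this confounding. Section 7.4.2 sends every SAE to the Medical Monitor whatever its attribution, and directs attention to the difficulty of separating rituximab, corticosteroid and exchange toxicity. SAEs graded unlikely or unrelated remain in the monthly report, and FDA receives all adverse events annually.

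These safeguards are real and limit the harm. They do not close the gap. The Medical Monitor checks categorizations against the protocol's own criteria, and an Unlikely correctly assigned under 7.3 passes that check. Monthly and annual reports preserve the record but do not replace immediate or 7-day notice.

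A reader might also infer more than the documents support:

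- **That all joint-cause events are lost.** Evenly shared causes stay Possible, and with several rivals rituximab can rank first at well under half.
- **That overlapping toxicity lists settle the grade.** They show that an alternative exists; whether it is more likely is decided case by case.
- **That exchange is always a same-day rival.** Section 5.1.4 governs infusions during exchange. Section 5.1.5 provides for the remaining doses after exchange has stopped.
- **That the related-event endpoint is biased downwards.** Sections 1.2.1 and 9.2 do not tie that endpoint to 7.3 or to any grade. Section 9.2 compares it with historical controls who, per the Abstract, were initially treated with exchange and corticosteroids, and a rituximab-only scale does not naturally fit them.

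**Conclusion.** The point stands in a narrow form. Because 7.3 grades by rank against an alternative and 7.2 by reasonable possibility, an unexpected SAE to which rituximab plausibly contributed can reach the local IRB within 24 hours and yet trigger neither immediate NHLBI notice nor the 7-day FDA report. This assumes that investigators apply 7.3 as written and that one alternative is ranked above rituximab.

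The size cannot be estimated from the documents. It is limited to unexpected SAEs with strong timing and a higher-ranked alternative, and those events are delayed or routed differently rather than lost. Any effect on the treatment-related endpoint is conditional on using 7.3 with a cut at Possible. What can be said without that condition is that the endpoint's scale and cut-off are undefined. The change is worth making because it is cheap and concerns prompt safety reporting.

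**What to change.** - **Section 7.3.** Define Possible as a reasonable possibility that rituximab caused or contributed to the event, even if another cause is as likely or more likely. Reserve Unlikely for events where a contribution is not plausible; poor timing can remain one reason for that view. Adjust the limb of Not Related on a much more likely alternative to match, so that the grades do not overlap.
- **Section 9.2.** State which scale and which cut-off grade define treatment-related, whether treatment means rituximab or the whole regimen, and how the definition applies to the historical controls.
- **Optional.** Record attribution to plasma exchange, corticosteroids and TTP separately from rituximab, allowing more than one.

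The cost is protocol wording and, for the optional item, additional case report form fields. The downside is that somewhat more events will be called related and a few more expedited reports will be filed.

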## 7.4 Reporting and Monitoring Adverse Events

Information about all adverse events that occur within 1 year after enrollment in subjects will be collected. The clinical course of AEs will be followed until a medical outcome is determined. Additional information that becomes available may be added to previously submitted AE reports at any time. Site investigators should follow their local IRB's guidelines in terms of reporting AEs to them. All AEs must be reported to Washington University's Clinical Coordinating Center (CCC) on designated case report forms (CRFs) to be provided by the sponsor-investigator.

### 7.4.1 Expedited Reporting of Serious Adverse Events

Serious adverse events (SAEs) are defined as AEs that cause death, a life-threatening adverse experience, or a persistent or significant disability/incapacity (i.e. Grade 4 and 5 events); inpatient hospitalization or prolongation of existing hospitalization; pregnancy abortion, or a congenital anomaly, birth defect, or cancer in a neonate/infant born to a female subject.

Serious adverse events must be reported by Clinical Center personnel to the Washington University CCC within 24 hours of the Clinical Center's awareness (Monday-Friday) by electronically mailing the completed Serious Adverse Event form and de-identified source documentation to [name] ([[contact]](mailto:[contact])) and [name], BSN ([[contact]](mailto:[contact])). Each Clinical Center will follow their local IRB reporting policy of AEs and SAEs. If a SAE is determined to be unexpected and possibly, probably, or definitively related to rituximab or to participation in the research study, it must be reported to the local IRB within 24 hours of the Clinical Center's awareness of the event. Data on all serious adverse events that occur in subjects will be collected through the end of their study participation (i.e. the full 2-year follow-up period).

#### **7.4.2 Monitoring of Serious and Unexpected Adverse Events**

Serious adverse events will be reported by the CCC to the Medical Monitor in an expedited manner, irrespective of the attribution of the event to the study drug/device/procedure/treatment. Serious adverse events will be promptly reviewed by the Medical Monitor. The Medical Monitor will review the categorizations of the SAE to verify consistency with protocol reporting criteria, and communicate with the site investigator if there are discrepancies or questions. The Medical Monitor has medical expertise relevant to the study protocol and may request the subject's treatment assignment when reviewing the adverse event. The Medical Monitor shall review the data with particular attention to the complexities of assessing toxicity due to rituximab, corticosteroids and PE in TTP subjects. The Medical Monitor is responsible for notifying the Principal Investigator (IND Holder) of any changes to the categorizations of serious adverse events and of any concerns regarding the frequency or type of adverse event(s). The NHLBI Project Officer will be notified immediately if a SAE is determined to be unexpected and possibly, probably, or definitively related to rituximab; additionally, information about the event will be included in the monthly summary report. If an event is determined to be unrelated or unlikely related to rituximab, it will still be included in the monthly summary report. The CCC will prepare monthly summary reports of all serious adverse events for review by the Medical Monitor, the Principal Investigator, and the NHLBI.

#### **7.4.3 Reporting Adverse Events to NHLBI**

Reports of accrual information, outstanding queries, serious adverse events, and protocol violations will be distributed to NHLBI monthly. Federal guidelines for reporting of Unanticipated Problems will be followed (see <http://www.hhs.gov/ohrp/policy/AdvEvtGuid.htm>).

#### **7.4.4 Reporting Adverse Events to FDA**

All serious adverse events that are unexpected and possibly, probably, or definitely related to the use of rituximab will be reported to FDA no later than 7 days from the sponsor-investigator's original receipt of the information. FDA will receive annual summaries of all adverse events.

### **8. CRITERIA FOR REMOVAL FROM PROTOCOL THERAPY AND OFF STUDY**

#### **8.1. Criteria for removal from Protocol therapy with adjuvant low dose rituximab**

- 1) Salvage Therapy before all four doses of rituximab are administered
- 2) Two or more exacerbations in the first 30 days after enrollment
- 3) Plasma Exchange is performed sooner than 12 hours after the end of rituximab infusion

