## DEFINITIONS

**Day 1:** The first day a subject receives plasma exchange for treatment of TTP.

**Treatment Response:** 2 consecutive days with platelet count  $\geq 150,000/\mu\text{L}$

**Durable Treatment Response:** Treatment Response that persists for  $\geq 30$  days after discontinuation of plasma exchange.

**Exacerbation:** Recurring TTP  $\leq 30$  days after a Treatment Response and discontinuation of plasma exchange.

[figure not shown]
**Refractory TTP:** Failure to achieve a Treatment Response by day 28, or failure to achieve a Durable Treatment Response by day 60.

**Composite Primary Endpoint:** Exacerbation or Refractory TTP.

**Relapse:** Recurring TTP  $> 30$  days after Treatment Response.

**Observation Period:** The interval of 2 years after a subject first achieves a Durable Treatment Response.

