#### **4. STUDY ENROLLMENT**

##### **4.1 Recruitment and screening**

Subjects will be recruited through the Transfusion Medicine or Hematology Consult services at Washington University and up to 5 additional sites. A potentially eligible subject will be identified by his or her physician. Once a potentially eligible subject is identified, and after the treating staff has obtained permission from the subject to be contacted, a member of the study staff will contact the subject, describe the study, and obtain consent.

After signing the consent form the subject will be assigned a study ID number and study staff will determine if the subject is eligible based on his or her medical history and laboratory results. A subject is considered enrolled in the study after the informed consent document is signed by the subject and the subject meets all eligibility criteria. Within one day (Monday-Friday) after enrollment, the site should submit a copy of the Inclusion/Exclusion Criteria Checklist that has been signed by a site investigator to the Washington University Clinical Coordinating Center.

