### **5.1.2 Administration**

Each study site will utilize its own supply of rituximab, and will store under conditions consistent with the drug's package insert. The prescribed dose of rituximab will be reconstituted in normal saline to a concentration no more than 4 mg/mL. Rituximab dose is fixed dose of 100 mg, given intravenously, repeated at one-week intervals for a total of four doses. Rituximab is to be administered only by slow intravenous infusion; it is not to be administered as an IV push or bolus. The infusion may be administered via a peripheral venous catheter; no central catheter is required. Treatment may be on an out-patient basis; in-patient hospitalization is not required. Each rituximab infusion bag will be labeled by the pharmacy as "Investigational Drug – ART Study". An Investigational Drug Accountability Log will be provided to each site by the sponsor-investigator and will be maintained by personnel at each study site. This Log will be updated by study personnel each time rituximab is dispensed by the pharmacy and a copy will be provided to the site research coordinator and the Washington University liaison. All expired or unused drug will be destroyed in accordance with local institutional practice.

Rituximab is to be infused every 7 days with a window of 5-9 days considered acceptable. If a dose is administered outside the 5-9 day window, then the schedule will be altered such that the next dose will be given 7 days later and any subsequent doses will be given at 7 day intervals.

The first rituximab infusion will be given as soon as possible after study eligibility is established but before the 5th plasma exchange.

The initial rituximab solution for infusion will be administered intravenously at an initial rate of 50 mg/hr. Subsequent rituximab infusion can be administered at an initial rate of 100 mg/hr.

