### 5.2.5 Treatment of Refractory TTP

The subject will be considered to have Refractory TTP if they do not have a Treatment Response by day 28, or do not have a Durable Treatment Response by day 60. The treatment of Refractory TTP will include resuming plasma exchange and corticosteroids. Additional salvage therapy is at the physician's discretion and can include full dose rituximab  $375 \text{ mg/m}^2$  weekly for 4 doses. Patient with Refractory TTP will be followed for 2 years with laboratory monitoring.

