## 5.3 Non-Protocol Treatments

The following medications and other treatments, which can influence the course of TTP, will be considered protocol violations and secondary endpoints if they are given after enrollment.

- 1) Immunosuppresses/cytotoxic agents, including:

- a. Cyclophosphamide
- b. Azathioprine
- c. Vincristine
- d. High dose corticosteroids (>1.5 mg/kg)

2) Calcineurin inhibitors, including:

- a. Cyclosporine A (brands - Sandimmune, Gengraf, Neoral)
- b. Tacrolimus (FK506) (brand - Prograf)
- c. Sirolimus (brand - Rapamune)

3) Anti-platelet agents:

Aspirin, ticlopidine, dipyridamole, NSAIDs, clopidogrel, and other anti-platelet agents may not be given for treatment of TTP per se, but may be administered when indicated for other conditions.

4) Cytokines/growth factors and megakaryocyte simulating drugs, including:

- a. Oprelvekin (IL-11) (Brand- Neumega)

5) Splenectomy

6) Staphylococcal protein A column treatment

7) Intravenous immunoglobulin (IVIG)

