#### **8.2. Off study criteria**

- 1) Death
- 2) Lost to follow up
- 3) Participation in other trials of investigational therapies

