### 9.2 Data analysis

Fisher Exact tests will be used to compare the incidence of the composite primary endpoint, Durable Treatment Response, Relapse, treatment-related adverse events and 4-week, 1-year and 2-year incidence of death between the treated group and historical controls. We will consider Chi-Square test to examine differences in the type and severity of adverse events between the treated group and historical controls.

The time to Durable Treatment Response and Relapse will be described by Kaplan-Meier estimators and log rank tests. The effects of patient characteristics will be evaluated with Cox proportional hazards models. Numbers of plasma exchanges to Durable Treatment Response will be compared with non-parametric tests (e.g. Kruskal-Wallis analysis of variance).

The value of ADAMTS13 biomarker data for predicting Exacerbation, Durable Treatment Response or Relapse will be analyzed by logistic regression. The relationship between ADAMTS13 biomarker parameters and platelet count, LDH or B cell levels will be investigated with linear regression models.

Rituximab levels and the extent of B cell depletion will be analyzed as stratified categorical data with Cochran-Mantel-Haenszel statistics.

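### A patient rescued by other treatment before responding, and durable by day 60, scores as event-free on low dose rituximab; section 9.2 should add a sensitivity analysis that counts salvage as an event in both groups

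*Combined protocol and SAP*

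**What the plan says.** The Definitions make the composite primary endpoint Exacerbation or Refractory TTP. Treatment Response is a platelet criterion. Exacerbation is a recurrence that follows a Treatment Response and the end of plasma exchange. Refractory TTP is "Failure to achieve a Treatment Response by day 28, or failure to achieve a Durable Treatment Response by day 60". None of these mentions other treatment.

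Salvage appears in four places:

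- Section 8.1 lists "Salvage Therapy before all four doses of rituximab are administered" as a reason to stop protocol therapy and attaches no other consequence.
- Section 8.2 gives three off-study reasons: death, loss to follow-up and "Participation in other trials of investigational therapies". Salvage is not among them.
- Section 5.3 lists agents and procedures "which can influence the course of TTP, will be considered protocol violations and secondary endpoints if they are given after enrollment". The list includes vincristine, cyclophosphamide, splenectomy and steroids above 1.5 mg/kg. It omits full dose rituximab.
- Section 5.2.5, once Refractory TTP is declared, says "Additional salvage therapy is at the physician's discretion and can include full dose rituximab". Section 5.2.6 says the same for relapse.

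Section 9.2 compares the composite, Durable Treatment Response and "4-week, 1-year and 2-year incidence of death between the treated group and historical controls" by Fisher exact tests. It has no rule for salvage.

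**The concern.** The trial asks whether low dose rituximab, added to exchange and steroids, lowers the rate of exacerbation or refractory disease. If the physician judges early that the regimen is failing and adds another drug, a later platelet recovery cannot be credited to low dose rituximab alone. As the endpoint is written, it is. The same patient also counts towards the secondary incidence of Durable Treatment Response.

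With 20 treated patients, each one is 5 percentage points. The control rate of 55% may carry the same ambiguity. The Abstract says the controls were treated initially with exchange and steroids, and section 2.4 calls full dose salvage rituximab the current standard of care. The documents do not say what later salvage the controls received or how it was scored. The size of the effect and its attribution are therefore at stake, and the primary result alone would not show it.

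**Working it through.** **1. Can the case arise?** Section 5.1.2 puts the first dose before the fifth exchange and then says "Rituximab is to be infused every 7 days with a window of 5-9 days considered acceptable". If exchange is daily (an assumption), the first dose falls on day 1 to 5.

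- At 7-day spacing, dose 4 falls 3 × 7 = 21 days later, on day 22 to 26.
- Across the 5 to 9 day windows it falls 15 to 27 days later, on day 16 to 32.

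Salvage before dose 4 can therefore come before day 28.

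**2. How is that patient scored?** Take salvage before any Treatment Response, with response by day 28.

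- Exacerbation: it needs an earlier response, so the salvage itself does not qualify. No later recurrence is assumed.
- Refractory, day 28 limb: response was reached, so not met.
- Refractory, day 60 limb: if exchange stops by day 28, 30 days of durability are complete by day 28 + 30 = 58, so not met.

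The patient is event-free and a Durable Treatment Response.

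**3. Who is not affected?** Patients salvaged after an exacerbation, or from day 28 without a response, are already events. So is anyone not durable by day 60.

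**4. The plan's own figure.** Section 9.1 has 55% against 10%, 40 controls and a 5% level (two-sided taken, as sidedness is not stated). The pooled normal approximation gives power 0.907 with 14 treated and 0.888 with 13, so the stated 14 reproduces. The sample size is not in dispute.

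**5. Sensitivity.** Inputs are 0.10 × 20 = 2 treated events and 0.55 × 40 = 22 control events. The number rescued is not documented, so 0 to 4 is an assumed range. Tests are two-sided Fisher exact; intervals are Newcombe 95%, control minus treated.

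Treated patients recounted, no controls recounted:

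| Rescued | Treated | Control | Difference (95% CI), points | p |
|---|---|---|---|---|
| 0 | 2/20 = 10% | 22/40 = 55% | 45 (20 to 61) | 0.0008 |
| 1 | 3/20 = 15% | 22/40 | 40 (14 to 57) | 0.005 |
| 2 | 4/20 = 20% | 22/40 | 35 (9 to 54) | 0.013 |
| 3 | 5/20 = 25% | 22/40 | 30 (3 to 50) | 0.032 |
| 4 | 6/20 = 30% | 22/40 | 25 (-2 to 46) | 0.100 |

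Both groups recounted at the same rate, as a share of all patients (1/20 = 2/40):

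| Rescued, treated and control | Treated | Control | Difference, points | p |
|---|---|---|---|---|
| 1 and 2 | 3/20 = 15% | 24/40 = 60% | 45 | 0.001 |
| 2 and 4 | 4/20 = 20% | 26/40 = 65% | 45 | 0.002 |
| 4 and 8 | 6/20 = 30% | 30/40 = 75% | 45 | 0.0017 |

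If rescue occurred only among controls, the difference would widen. For example, 2/20 against 24/40 is 60 - 10 = 50 points.

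**6. Dropping rescued patients instead.** Removing one to four of them gives 2/19, 2/18, 2/17 and 2/16 against 22/40, with p = 0.0015, 0.0017, 0.003 and 0.006.

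**The case against.** **Salvage belongs to patients who are already events.** Sections 5.2.5 and 5.2.6 describe it only after Refractory TTP or relapse, and the 8.1 criterion can be read as salvage after an early exacerbation, or from day 28 with dose 4 pending. This stands as a limit on the size of the group. It does not close the gap, because 8.1 is not confined to those patients and dose 4 normally falls before day 28.

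**Section 5.3 already tracks most rescue agents.** It makes them protocol violations and secondary endpoints, and section 7.4.3 sends violations to NHLBI monthly. That helps transparency. It leaves the primary endpoint unchanged and omits full dose rituximab.

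**Scoring the outcome whatever else was given is a legitimate choice.** Making salvage an event lets an unblinded physician's decision determine the outcome, set against controls whose threshold for salvage may have differed. This stands, and it is why the platelet-based definition should remain primary.

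**A reader might infer more than the documents support:**

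- That the result is biased in favour of rituximab. Scoring of salvage in the controls is not stated, and equal rescue rates leave the difference at 45 points.
- That four rescues would reverse the result. At 6/20 against 22/40 the difference still favours treatment by 25 points; significance is lost, nothing more.
- That patients removed under 8.1 drop out of the analysis. Section 4.1 says "A subject is considered enrolled in the study after the informed consent document is signed" and eligibility is met, and 8.2 keeps such patients on study, so the natural reading is that they stay in. Section 9.2 speaks only of the treated group. That is a missing detail, and exclusion would keep p at or below 0.006 in these examples.

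**Conclusion.** The gap is real and narrow. Following the plan as written credits to low dose rituximab a patient whom other treatment rescued before any response, provided that patient responds by day 28, does not exacerbate and is durable by day 60.

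The size cannot be fixed from the documents. Under the assumed range of one to three rescued treated patients and no recounted controls, the difference falls from 45 points to between 40 and 30 and remains significant; four would lose significance. These figures assume that the planned rates are observed exactly. The net direction is unknown. The estimated effect and its attribution are more exposed than the significance test. This is a cheap improvement and does not undermine the design.

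**What to change.** Keep the Definitions as the primary endpoint. Before outcomes are analysed, add one paragraph to section 9.2:

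1. A sensitivity analysis counts as a composite event any salvage given for lack of response or worsening TTP before a Durable Treatment Response. Salvage means full dose rituximab, or any section 5.3 agent or procedure used to treat TTP, including steroids above 1.5 mg/kg. Premedication under section 5.1.3 does not count; its single 100 mg dose would exceed 1.5 mg/kg in anyone lighter than 100/1.5 = 67 kg.
2. The same rule is applied to the 40 control charts, and the control rate under both definitions is reported beside the 55%.
3. Patients removed under section 8.1 stay in the denominator.
4. The report states whether the conclusion holds under both definitions.

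The cost is a re-read of 40 charts for salvage, its date and its reason. Treated patients already have a medication log, but the reason for salvage, or a splenectomy, may need a source check. The added analysis depends on an unblinded physician's decision and could move the result in either direction.
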